#### 3. Major Hemorrhage

Major hemorrhage is defined as any hemorrhagic event that is serious, or Grade  $\geq$  3 in severity, or that is a CNS hemorrhage (any severity grade).

# Search Strategy:

- I. Use standardized MedDRA query:
  - o Haemorrhage terms (excluding laboratory terms) (SMQ) [20000039]
- II. Identify Major Events that are a subset of the Haemorrhage SMQ:
  - o Grade >3 AE
  - Any serious adverse event
  - o All grades of CNS hemorrhage

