For PHL and HL, the elevation in transaminases must precede or be coincident with (i.e., on the same day) the elevation in total bilirubin, but there is no specified timeframe within which the elevations in transaminases and total bilirubin must occur.

IDENTIFICATION OF POTENTIAL HY'S LAW CASES

Laboratory data must be comprehensively reviewed by the investigator for each subject to identify laboratory values meeting the following criteria:

- ALT ≥3 x ULN
- AST ≥3 x ULN
- Total bilirubin ≥2 x ULN

When the identification criteria are met from central or local laboratory results, the investigator will perform the following:

- Notify the sponsor representative/Medical Monitor by telephone and report the PHL case as an SAE of Potential Hy's law: seriousness criteria "Important medical event" and causality assessment "yes/related" or in accordance with the clinical study protocol as appropriate.
- Request a repeat of the test (new blood draw) without delay
- Complete the appropriate unscheduled laboratory electronic Case Report Form (eCRF) module(s)
- Perform follow-up on subsequent laboratory results according to the guidance provided in the clinical study protocol, as applicable

REVIEW AND ASSESSMENT OF POTENTIAL HY'S LAW CASES

The instructions in this section should be followed by the investigator for all cases where PHL criteria are met.

As soon as possible after the biochemistry abnormality is initially detected, the study Medical Monitor and the Investigator will review available data, to agree whether there is an alternative explanation for meeting PHL criteria other than DILI caused by the IMP and to ensure that timely analysis and reporting to health authorities within 15 calendar days from the date PHL criteria were met.

Where there is an agreed alternative explanation for the ALT or AST and total bilirubin elevations, a determination of whether the alternative explanation is an AE will be made and, subsequently, whether the AE meets the criteria for an SAE:

- If the alternative explanation is **not** an AE, record the alternative explanation on the appropriate eCRF.
- If the alternative explanation is an AE/SAE, update the previously submitted PHL SAE accordingly with the new information (reassessing event term, causality, and seriousness criteria) following the sponsor's standard processes.

If it is agreed that there is **no** explanation that would explain the ALT or AST and total bilirubin elevations other than the IMP, then:

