#### 2. Events of Clinical Interest

The Events of Clinical Interest (ECIs) have been identified based on preclinical findings, emerging data from clinical studies relating to acalabrutinib, and pharmacological effects of approved Bruton's tyrosine kinase (BTK) inhibitors. The adverse events (AEs) selected for dedicated analysis were evaluated using Standardized MedDRA Queries (SMQs), where available, by System Organ Classes (SOCs), or by Sponsor-defined baskets of MedDRA Adverse Event Grouped Terms.

Category	Subcategory	Definition
Cardiac events		SOC Cardiac disorders
	Atrial fibrillation	PT Atrial fibrillation
		PT Atrial flutter
	Ventricular	PT Torsade de pointes
	tachyarrhythmias	PT Ventricular arrhythmia
		PT Ventricular extrasystoles
		PT Ventricular fibrillation
		PT Ventricular flutter
		
 
PT Ventricular tachyarrhythmia
 

		PT Ventricular tachycardia
Cytopenias –		SMQ Haematopoietic erythropenia [narrow +
Anemia		broad]
Cytopenias – Leukopenia		SMQ Haematopoietic leukopenia [narrow + broad]
	Neutropenia	PT Band Neutrophil count decreased
		PT Band neutrophil percentage decreased

		•	PT Cyclic neutropenia
		•	PT Febrile Neutropenia
		•	PT Granulocyte count decreased
		•	PT Granulocyte percentage decreased
		•	PT Idiopathic neutropenia
		•	PT Neutropenia
		•	PT Neutropenic infection
		•	PT Neutropenic sepsis
		•	PT Neutrophil count decreased
		•	PT Neutrophil percentage decreased
	Other leukopenia	•	SMQ Haematopoietic leukopenia [narrow + broad] excluding PTs for neutropenia above
Cytopenias - Thrombocytopenia		•	SMQ Haematopoietic thrombocytopenia [narrow + broad]
Hemorrhage		•	SMQ Haemorrhage terms (excl laboratory terms)
	Major hemorrhage	•	As per definition (see Section 3 below)
Hepatotoxicity		•	SMQ [narrow] Hepatic failure, fibrosis and cirrhosis and other liver damage-related conditions
		•	SMQ [narrow] Hepatitis, non-infectious
		•	SMQ [narrow] Liver related investigations signs
Hypertension		•	SMQ Hypertension [narrow]
Infections		•	SOC Infections and infestations
Interstitial lung disease/Pneumonitis		•	SMQ [narrow] Interstitial lung disease
Second primary malignancies		•	SMQ Malignant tumours (including Haematological malignant tumours SMQ and Non-haemoatological malignant tumours SMQ) SMQ Malignant lymphomas [narrow] SMQ Myelodysplastic syndrome [narrow]
	Second primary malignancies (excluding non melanoma skin)	•	The above excluding PTs mapping to HLT Skin neoplasms malignant and unspecified (excluding melanoma)

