#### 2. Additional Criteria for Narratives:

 Subjects who fulfill ECI (see Appendix 1 for definitions) criteria and additional criteria for narratives as described below:

Note: the window for qualifying events for narratives is from first date of study drug to last date of study drug + 30 days or start of new anticancer therapy, whichever comes first. Beyond this window, narratives should only be provided for any related SAEs and for clinically significant AEs as judged by medical monitor.

ECI Category Name	ECI Subcategory Name	Additional Criteria for Narratives	
Cardiac events	Atrial fibrillation	

Grade 3 and 4 PT Atrial fibrillation

Grade 3 and 4 PT Atrial flutter

	
Hemorrhage	Major hemorrhage	Same as ECI definition. Refer to Appendix 1 Section 2	
Hepatotoxicity		
 
Subjects who fulfill biochemical Hy's law criteria defined as below:
 
≥3×ULN AST or
 
≥3×ULN ALT and
 
≥2×ULN total bilirubin where bilirubin increased of ≥2xULN either coincides with ALT/AST elevations or follow them within 8 days
 
Grade 4 non-serious hepatotoxicity
 
	
Second primary malignancies	Second primary malignancies (excluding non melanoma skin)	Below SMQs excluding PTs mapping to HLT Skin neoplasms malignant and unspecified (excluding melanoma)  SMQ Malignant tumours (including Haematological malignant tumours SMQ and Non- haemoatological malignant tumours SMQ  SMQ Malignant lymphomas [narrow]  SMQ Myelodysplastic syndrome [narrow]	
Tumor lysis syndrome		Same as ECI definition. Refer to Appendix 1 Section 2	

AE=adverse event; ALT=alanine aminotransferase; AST=aspartate aminotransferase; HLT=high-level term; ISS=integrated safety summary; PT=preferred term; SAE=serious adverse event; SMQ=Standardised MedDRA Query; ULN=upper limit of normal.

MedDRA version 24.1

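### The SAP defines major hemorrhage as Grade 3 or higher but its search strategy selects only Grade above 3, so a non-serious, non-CNS Grade 3 bleed is left out of the count

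*SAP*

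**What the plan says.** **Definition.** SAP Appendix 1, Section 3 opens: "Major hemorrhage is defined as any hemorrhagic event that is serious, or Grade" 3 or above, or a CNS hemorrhage of any grade.

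**Search.** The search strategy under the same heading starts from the Haemorrhage SMQ (excluding laboratory terms). Its second step is "Identify Major Events that are a subset of the Haemorrhage SMQ", with three limbs: an adverse event of Grade >3, "Any serious adverse event", and "All grades of CNS hemorrhage".

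**Where it is used.** The Events of Clinical Interest (ECI) table in Appendix 1, Section 2 fills the major-hemorrhage row with "As per definition (see Section 3 below"), and SAP Section 7.7.2 reports subject incidence for these categories. The narrative table in SAP Appendix 2 sends the reader back to the ECI definition.

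**Hy's law, for the minor point.** One of the additional narrative criteria in SAP Appendix 2 requires a bilirubin rise that "either coincides with ALT/AST elevations or follow them within 8 days". Protocol Appendix 7 requires the transaminase rise to come first or on the same day, but says "there is no specified timeframe within which the elevations in transaminases and total bilirubin must occur".

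**The concern.** A programmer who follows the numbered search steps and one who follows the sentence above them will produce different major-hemorrhage counts from the same data. The search is the narrower of the two, so following it can only reduce the count.

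Protocol Section 3.7.1 lists hemorrhage as an important identified risk of acalabrutinib, with fatal events seen. The cohorts are small, so one subject moves the percentage visibly. The event at issue can occur, because protocol Section 6.2.2 says that severity and seriousness are separate properties. Being non-serious, such a bleed does not qualify for a narrative through the SAE route in SAP Appendix 2 either. It would need to have led to discontinuation of study drug.

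**Working it through.** There is no stated figure to reproduce. The check compares the two rules over every combination of grade (1 to 5), seriousness and site: 5 × 2 × 2 = 20 combinations.

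- Definition: serious, or grade ≥3, or CNS.
- Search as printed: serious, or grade >3, or CNS.

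| Grade | Serious (CNS or not) | Non-serious, CNS | Non-serious, non-CNS |
|---|---|---|---|
| 1 | both select | both select | neither selects |
| 2 | both select | both select | neither selects |
| 3 | both select | both select | **definition only** |
| 4 | both select | both select | both select |
| 5 | both select | both select | both select |

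The serious column stands for 10 combinations and each of the others for 5. The definition selects 10 + 5 + 3 = 18, and the search selects 10 + 5 + 2 = 17. The one difference is Grade 3, non-serious, non-CNS. The search selects nothing that the definition excludes. With the severity limb set to ≥3, the two agree in all 20.

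**Size per subject.** SAP Section 3.2 gives up to 40 subjects in Part 2 Cohort 1 and about 26 to 32 in Part 3.

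- Part 2: 1/40 = 2.5 percentage points.
- Part 3: 1/32 = 3.1 points to 1/26 = 3.8 points.

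**Chance that it matters.** The documents give no rate for such bleeds, so the per-subject rates p below are assumptions. The chance of at least one affected subject is 1 − (1 − p)^n. For n = 40:

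- p = 1%: 1 − 0.99^40 = 33%
- p = 2%: 1 − 0.98^40 = 55%
- p = 5%: 1 − 0.95^40 = 87%

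**Hy's law.** Counting days from the transaminase rise to the bilirubin rise, a lag of 0 to 8 days meets both texts. A lag of 9 days or more meets protocol Appendix 7 but not the SAP criterion.

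**The case against.** **The symbol may be an artefact.** The SAP text was machine-read and has visible misreadings elsewhere, so the printed > could be a ≥ that lost its underline. This stands as a reason to look at the PDF first. Against it, ≥ survives in many other places in the SAP, including the exposure definitions in Section 7.5.3 and the liver criteria in Appendix 2.

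**The cross-references point to the definition.** The ECI row refers to the definition, and the narrative table repeats the ECI definition. On that reading the intended threshold is clear and the search line is a slip. This is fair as to intent. But both references end in a section that holds both thresholds, and the search strategy is the part written as instructions for selecting records.

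**Little disappears.** This also stands. A reader might infer that these bleeds vanish from the safety report, and the documents do not support that. They remain in the overall hemorrhage ECI, which uses the whole SMQ, and in the treatment-emergent adverse event summaries by severity (SAP Section 7.7.1).

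**Hy's law.** A reader might infer that the 8-day limit causes qualifying liver cases to be missed. That does not follow, for four reasons.

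- Protocol Appendix 7 has every potential Hy's law case reported as an SAE, and the primary criteria in SAP Appendix 2 give every death and non-fatal SAE a narrative. The limit is only an additional narrative trigger, and it feeds no incidence table.
- ALT, AST and bilirubin are in the same chemistry panel (protocol Section 4.1.12). If the transaminase is still raised when bilirubin reaches its threshold, the two coincide.
- It is tempting to argue that two consecutive scheduled draws after Cycle 1 can never fall within 8 days. Protocol Appendices 5 and 6 also schedule chemistry at the End of Treatment visit, which can fall within 8 days of a cycle draw.
- The SAP is not shown to implement Appendix 7. It is written to protocol Amendment 6 and states its own criterion without citing that appendix. In the Canadian version 6.1, Appendix 7 was the pandemic appendix, which suggests, though only by inference from the numbering, that the Hy's law appendix came later.

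**Conclusion.** The major-hemorrhage discrepancy is real as printed. The search omits exactly one type of event that the definition includes, the non-serious, non-CNS Grade 3 bleed. Followed literally, it can only lower the major-hemorrhage count, by 2.5 points per affected subject in Part 2 and 3.1 to 3.8 points in Part 3, and it removes the narrative trigger for those events.

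This rests on two assumptions: that the PDF also shows >, and that programming follows the search step rather than the sentence above it. The number of affected subjects is unknown. The per-subject shares are a scale, not an estimate of the effect.

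The Hy's law difference is one of wording, to be reconciled. It is not evidence that cases go unreported. What remains is limited to a case with a lag of 9 days or more that the investigator did not report as an SAE.

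**What to change.** Check the source PDF at the second step of the search strategy in SAP Appendix 1, Section 3. If it shows >, change the severity limb to Grade ≥3 so that it matches the definition directly above, and confirm that the program for the major-hemorrhage row and its narratives uses that threshold. The cost is one character in the SAP, a check of one derivation, and possibly a few more narratives.

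Separately, and at lower priority, reconcile the time criterion in SAP Appendix 2 (hepatotoxicity) with current protocol Appendix 7, or add a sentence saying why the narrative trigger differs from the SAE-reporting rule. This is a text edit, again with perhaps a few extra narratives.

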## **CNS Hemorrhage Preferred Terms**

- Acute haemorrhagic leukoencephalitis
- Basal ganglia haematoma
- Basal ganglia haemorrhage
- Basilar artery perforation
- Brain contusion
- Brain stem haematoma
- Brain stem haemorrhage
- Brain stem microhaemorrhage
- Central nervous system haemorrhage
- Cerebellar haematoma
- Cerebellar haemorrhage
- Cerebellar microhaemorrhage
- Cerebral aneurysm perforation
- Cerebral aneurysm ruptured syphilitic
- Cerebral arteriovenous malformation haemorrhagic
- Cerebral artery perforation
- Cerebral cyst haemorrhage
- Cerebral haematoma
- Cerebral haemorrhage
- Cerebral haemorrhage foetal
- Cerebral microhaemorrhage
- Encephalitis haemorrhagic
- Epidural haemorrhage
- Extradural haematoma
- Extraischaemic cerebral haematoma
- Haemorrhage intracranial
- Haemorrhagic cerebral infarction
- Haemorrhagic stroke
- Haemorrhagic transformation stroke
- Intracerebral haematoma evacuation
- Intracranial haematoma
- Intracranial tumour haemorrhage
- Intraventricular haemorrhage
- Meningorrhagia
- Ocular retrobulbar haemorrhage
- Optic disc haemorrhage
- Optic nerve sheath haemorrhage
- Pituitary apoplexy
- Pituitary haemorrhage
- Putamen haemorrhage
- Retinal aneurysm rupture
- Retinal haemorrhage
- Retinopathy haemorrhagic
- Ruptured cerebral aneurysm
- Spinal cord haematoma
- Spinal cord haemorrhage
- Spinal epidural haematoma
- Spinal epidural haemorrhage
- Spinal subarachnoid haemorrhage
- Spinal subdural haematoma

# ACE-LY-003 Parts 2-3 Statistical Analysis Plan Version 1.0: 31Mar2022

- Spinal subdural haemorrhage
- Subarachnoid haematoma
- Subarachnoid haemorrhage
- Subdural haematoma
- Subdural haematoma evacuation
- Subdural haemorrhage
- Subgaleal haematoma
- Subgaleal haemorrhage
- Subretinal haematoma
- Thalamus haemorrhage
- Traumatic intracranial haematoma
- Traumatic intracranial haemorrhage
- Vertebral artery perforation

# **APPENDIX 2 – Search Strategy for Narratives**

# 1. Primary Criteria for Narratives:

• All deaths (regardless of cause), other non-fatal SAEs, AESIs (see Appendix 1 for definitions), AEs that led to discontinuation from study drug, pregnancies

#### 2. Additional Criteria for Narratives:

 Subjects who fulfill ECI (see Appendix 1 for definitions) criteria and additional criteria for narratives as described below:

Note: the window for qualifying events for narratives is from first date of study drug to last date of study drug + 30 days or start of new anticancer therapy, whichever comes first. Beyond this window, narratives should only be provided for any related SAEs and for clinically significant AEs as judged by medical monitor.

ECI Category Name	ECI Subcategory Name	Additional Criteria for Narratives	
Cardiac events	Atrial fibrillation	

Grade 3 and 4 PT Atrial fibrillation

Grade 3 and 4 PT Atrial flutter

	
Hemorrhage	Major hemorrhage	Same as ECI definition. Refer to Appendix 1 Section 2	
Hepatotoxicity		
 
Subjects who fulfill biochemical Hy's law criteria defined as below:
 
≥3×ULN AST or
 
≥3×ULN ALT and
 
≥2×ULN total bilirubin where bilirubin increased of ≥2xULN either coincides with ALT/AST elevations or follow them within 8 days
 
Grade 4 non-serious hepatotoxicity
 
	
Second primary malignancies	Second primary malignancies (excluding non melanoma skin)	Below SMQs excluding PTs mapping to HLT Skin neoplasms malignant and unspecified (excluding melanoma)  SMQ Malignant tumours (including Haematological malignant tumours SMQ and Non- haemoatological malignant tumours SMQ  SMQ Malignant lymphomas [narrow]  SMQ Myelodysplastic syndrome [narrow]	
Tumor lysis syndrome		Same as ECI definition. Refer to Appendix 1 Section 2	

AE=adverse event; ALT=alanine aminotransferase; AST=aspartate aminotransferase; HLT=high-level term; ISS=integrated safety summary; PT=preferred term; SAE=serious adverse event; SMQ=Standardised MedDRA Query; ULN=upper limit of normal.

MedDRA version 24.1

